## 9. HYPOTHESIS

[figure not shown]
1. Replacing SSBs with NSBs or water will change the diversity of gut microbiome after four weeks in regular SSB drinkers.
2. Replacing SSBs with NSBs or water will increase glucose tolerance after four weeks in regular SSB drinkers.
3. Replacing SSBs with NSBs or water will decrease body weight, reduce blood pressure, improve glucose and insulin regulation, decrease blood lipids, decrease ectopic fat, decrease liver fat, decrease body adiposity, and improve diet quality after four weeks in regular SSB drinkers.

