## 10. METHODS

**10.01 Trial Design.** We will conduct a single-centre, open label, randomized controlled crossover trial with three four-week intervention phases (SSB, NSB, water) comparing the effect of replacing SSBs with NSBs or water on the gut microbiome and glucose tolerance. A cross-over design was selected due to the high inter-individual heterogeneity in gut microbiome [25]. Prior to randomization, participants will undergo a ≥2-week run-in phase

to gather data on SSB consumption prior to study start. Each participant will then act as their own control receiving the 3 interventions in random order, each separated by a  $\geq 4$ -week wash-out phase (Figure 1). We will collect fecal samples from participants and conduct Oral Glucose Tolerance Tests (OGTTs) before the start and at the end of each intervention for gut microbiome analysis and glucose tolerance. All study visits will occur in Toronto at the Clinical Nutrition and Risk Factor Modification Centre at St. Michael's Hospital. The microbiome analysis and the objective biomarkers of SSBs assays will be performed at the Department of Nutritional Sciences, University of Toronto; plasma glucose analysis will be performed at the Banting and Best Diabetes Center (BBDC), University of Toronto; plasma insulin analysis and other blood analyses (for a selected sample using a multiplex kit for adiponectin, adiponisin, C-Peptide, Ghrelin, GIP, GLP-1, Glucagon, Insulin, leptin, PAI-1, Resistin and Visfatin) will be conducted at the Guelph Research and Development Centre, Ontario, Canada. Lipid analyses will be performed at St. Michael's Hospital Core Lab.

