#### **10.04 Sample Size (Power) Calculation.**

The study will be performed in a total of 81 participants. It is powered to show a difference between the water, NSB, and SSB arms in 60 participants in the two primary outcomes. Assuming a drop-out rate of 20 percent, we

would need 75 participants in order to have the power to detect a difference. Since our final recruitment strategy resulted in a large number of participants who made it through the run-in phase, we decided to increase our recruitment in order to replace drop outs and thus will recruit 81 participants.

One primary outcome is in beta diversity of the gut microbiome communities of the participants between water and NSB groups via 16S ribosomal rRNA gene sequencing. We used the micropower R package to compute sample size based upon the power of 16S tag sequencing that can be analyzed using pairwise weighted UniFrac distances [28]. UniFrac is a distance metric based upon the unique fraction of branch length in a phylogenetic tree built from two sets of taxa. Comparison of microbiome samples is performed via weighted UniFrac, which considers the relative abundance of taxa. We simulated the within-group distance as 0.2, and the standard deviation (SD) of within-group distances as 0.07. To detect a weighted UniFrac distance of 0.04, which is smaller than the effect observed in a study of Suez et al. [29] (0.05 derived from figure 5), and considering it is a cross-over study with a within-person correlation of 0.7, and taking into account multiple arms we calculated that for above 95 percent power we would need 60 participants in this study. Assuming a loss of 20 percent, we will recruit 75 participants. We are confident about detecting an alteration in gut microbiome diversity if it exists as previous studies show that small changes in diet causes significant alteration in gut microbiome taxa over a much shorter period (5 to 7 days) in fewer individuals (10 to 25 people) [25, 30].

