Another primary outcome is glucose tolerance, as measured by incremental Area Under the Curve (iAUC) from a 2-hour 75g OGTT. With 60 participants we will have 89 percent power (assuming absolute numbers for mean and SD from our recent unpublished randomized trial) to detect a 20% change in mean iAUC between the water and NSB group if the direction of change is similar to Suez et al. [29] while assuming a within-person correlation of 0.7 and taking into account the three comparisons. The 20% difference for glucose iAUC is based on the minimally important difference proposed by Health Canada to support postprandial blood glucose response reduction claims [31].

This power calculation takes into account adjustment for multiple testing for both primary outcomes using the Benjamini-Hochberg procedure, which is a suggested method by the Food and Drug Administration in its “Multiple Endpoints in Clinical Trials Guidance for Industry” [32]. Benjamini-Hochberg procedure is a step-down method that controls for false discovery rate, while maintaining high power [33, 34]. We will implement a truncated Benjamini-Hochberg method with parallel gatekeeping in which some portion of the unused alpha from each step is reserved for passing to the secondary outcome family if any of the primary outcome is significant. The alpha levels calculated for the primary outcomes is given in table 2. The study is also powered to show a difference between the three arms for secondary outcomes with an  $\alpha=0.0125$ , the lowest possible starting  $\alpha$  for secondary outcomes based upon the truncated Benjamini-Hochberg procedure.

Sub-study: 1H-MRS will be performed in 25 subjects to assess intrahepatic and intramuscular fat. We will have 99% to show a difference in liver fat of 5% between the water and NSB arm for both hepatic and muscle fat assuming a between group SD of 4%, with a correlation of 0.65 and alpha of 0.05.

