**Table 2. Power calculation for primary outcomes between water and NSB arms**

Outcome type	Outcome	Mean change	SD	Correlation	N	Alpha*	Power (Beta)	N (corrected for 20% loss to follow up)
Primary outcomes family								

Primary	Microbiome UniFrac Distance	0.04	0.07	0.7	60	0.0375	98%	75
Primary	Glucose iAUC	44.81 mmol/L/min (20%)	113 mmol/L/min	0.7	60	0.025	89%	75

P-value order will be from largest to smallest.

**10.05 Recruitment.** Participants will be recruited through postings and flyer handouts at St. Michael's Hospital, the University of Toronto, local clinics, and surrounding areas, advertisements in newspapers and on transit, and online listings on Craigslist and Kijiji. Some participants will complete a Survey Monkey to assess general eligibility. We will be utilizing a digital marketing group, TrialFacts, to launch a campaign to recruit participants. TrialFacts works exclusively with research groups to provide specialized patient recruitment services for clinical trials. Participants will be screened first by telephone. Eligible participants will be called in for an information session on the study including being provided the consent form. Those that wish to participate will provide written consent and will subsequently have an in-person screening including blood work. Based on our most recent FACE trial (NCT02459834), we estimate a recruitment rate of 1-2 participants/week and therefore plan to recruit all the participants within a 6-month period. **[name]** will organize the recruitment. Our **MSc candidate #1 ([name], RD)** and our **Research Coordinator** will conduct the screening.

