### **11. Statistical Analysis**

Data will be analyzed according to an intention to treat (ITT) principle using mixed models in STATA 14 (StataCorp, Texas, USA). Sensitivity analysis will be performed on the basis of complete data availability for primary endpoints. A separate sensitivity analysis will be performed on the basis of antibiotic use during the trial.

**Primary outcomes.** Repeated measures mixed effect models will be used to assess changes in the two primary outcomes i) beta diversity and ii) glucose iAUC between the groups. Pairwise comparisons between interventions will be performed using Tukey-Kramer adjustment or other appropriate statistics. For all primary outcomes effect modification by sex will be explored. We will use the truncated Benjamini-Hochberg false discovery rate controlling method with parallel gatekeeping procedure to correct for multiple comparisons for all primary outcomes [32].

**Secondary outcomes.** Repeated measures mixed effect models be used to assess changes in weight, waist circumference, fasting glucose, 2hr plasma glucose, and MATSUDA. Pairwise comparisons between interventions will be performed using Tukey-Kramer adjustment or other appropriate statistics. For all secondary outcomes

effect modification by sex will be explored. We will use the truncated Benjamini-Hochberg false discovery rate controlling method with parallel gatekeeping procedure to correct for multiple comparisons for all secondary outcome comparisons [33] if at least one primary outcome reaches significance. If none of the primary outcomes reach significance, the secondary outcomes will be analyzed as exploratory variables with no adjustment for false discovery rate.

**Exploratory and adherence outcomes.** Repeated measures mixed effect models will be used to assess changes in all exploratory outcomes without controlling for false discovery rate. Pairwise comparisons between interventions will be performed using Tukey-Kramer adjustment or other appropriate statistics. Effect modification by sex will be explored.

**Subgroup Analysis.** A priori analysis will be conducted by age, sex, ethnicity, baseline BMI, baseline WC, baseline FPG, baseline 2hPG (OGTT), baseline iAUC, medication use, sweetener blend (intervention), beverage type (intervention), and background sweetener use.

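### With three beverages, a closed pairwise test keeps Tukey-Kramer's error control and adds about 4 to 5 points of NSB-water glucose power, unless the SSB mean lies between the other two

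*Combined protocol and SAP*

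**What the plan says.** Section 11 covers the pairwise beverage comparisons with one sentence, repeated for primary, secondary and exploratory outcomes: "Pairwise comparisons between interventions will be performed using Tukey-Kramer adjustment or other appropriate statistics". It names no stepwise or closed procedure and excludes none. A second layer sits on top for the two primary outcomes: "We will use the truncated Benjamini-Hochberg false discovery rate controlling method with parallel gatekeeping procedure to correct for multiple comparisons for all primary outcomes". The same layer applies to the secondary outcomes if at least one primary outcome is significant.

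Section 10.04 sizes glucose incremental area under the curve (iAUC) on the NSB-water contrast: "With 60 participants we will have 89 percent power", "while assuming a within-person correlation of 0.7 and taking into account the three comparisons". The power table there (the first of two tables numbered 2) gives alpha 0.025 for glucose and 0.0375 for UniFrac distance. No mean is assumed for SSB. Its expected position appears only in Hypothesis 2 of section 9: "Replacing SSBs with NSBs or water will increase glucose tolerance after four weeks in regular SSB drinkers".

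**The concern.** Single-step Tukey-Kramer holds every one of the three pairs to the critical value that protects the largest of them. With only three means that is more than familywise control requires. If any two of the three pairwise null hypotheses are true, all three are true, so the three-way penalty has to be paid only once, on the most extreme pair. After that rejection at most one true pairwise null can remain, and each other pair can be tested at the full alpha for the outcome.

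The contrast that pays unnecessarily is any pair that is not the most extreme. If SSB is the worst beverage for glucose tolerance, NSB-water is such a pair, and it is the contrast on which the trial was sized. Power given up there also makes a null NSB-water result harder to interpret, and section 12 presents that comparison as the trial's purpose.

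**Working it through.** **Inputs** (section 10.04 and its power table): n = 60, each person receiving all three beverages; difference 44.81; SD 113; within-person correlation 0.7; alpha 0.025 for glucose iAUC. Assumed here: two-sided tests (the plan does not say), complete data on 60, equal correlation between all pairs of periods, and residual df (60 − 1) × (3 − 1) = 118.

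**1. Reproduce the plan's 89%.**
- SD of a within-person difference = 113 × √(2 × (1 − 0.7)) = 87.53.
- Standard error = 87.53 / √60 = 11.30.
- Noncentrality = 44.81 / 11.30 = 3.965.
- At 0.025/3 = 0.00833, power is 88.7% (59 df), 89.8% (118 df) or 90.8% (normal). This matches 89%.
- At an undivided 0.025, power is 94.9%, 95.4% or 95.8%. This does not match.

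So the stated 89% already divides alpha by three.

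**2. Single-step Tukey-Kramer.** The studentized range for 3 means and 118 df at 0.025 gives a critical |t| of 2.645, equivalent to testing NSB-water at a two-sided p of about 0.0093. The unadjusted critical value is 2.270. Power is 90.4%.

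**3. Closed test.** A pair is rejected if the largest |t| exceeds 2.645 and that pair's own |t| exceeds 2.270. Any pair that Tukey-Kramer rejects has |t| above 2.645, so it passes both conditions. The closed test therefore never rejects less than Tukey-Kramer.

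**4. NSB-water power by position of the SSB mean** (1,000,000 simulated trials per row, alpha 0.025, 118 df):

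| SSB mean relative to the water-NSB interval | Closed test | Gain over 90.4% |
|---|---|---|
| Outside by 50% or more of the difference | 95.4% | 5.0 points |
| Outside by 25% | 95.2% | 4.8 points |
| Equal to water or to NSB | 94.1% | 3.7 points |
| A quarter of the way inside | 91.9% | 1.5 points |
| Midway | 90.9% | 0.5 points |

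**5. Error control.** Under the global null the simulated familywise error is 0.0249. With NSB and water equal and SSB far away, the error on NSB-water is 0.0250. Both agree with the nominal 0.025.

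**6. Beta diversity.** From the power table, 0.07 × √0.6 / √60 = 0.0070, and 0.04 / 0.0070 = 5.71. Even at 0.0375/3 = 0.0125 a simple paired calculation gives over 99.8%. That is not the simulation behind the plan's 98%, but either figure leaves little to gain.

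**7. Secondary outcomes.** The documents give no mean or SD for any of them, so no gain can be computed.

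**The case against.** The case for leaving the text alone is substantial.

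- **The plan does not commit to single-step Tukey-Kramer.** The words after that name already allow a closed test. This stands, and it rules out calling the sentence an error. It does not remove the point: a more powerful rule chosen after results are known would not be credible in an open-label trial, so the gain is secured only if the rule is written down first.
- **Nothing is invalid or underpowered.** Tukey-Kramer controls the within-outcome error, stated power is 89% after the three-comparison penalty, and the plan recruits 81 rather than 75. This stands in full.
- **The gain depends on an SSB mean the plan never gives.** This stands. Hypothesis 2 places SSB as the extreme arm for glucose tolerance. Hypothesis 1 gives no ordering for diversity, and Hypothesis 3 concerns no primary outcome.
- **A closed rule can be written badly.** Gating on the largest raw difference can do worse than Tukey-Kramer when standard errors differ. With assumed correlations of 0.7 for NSB-water and 0.5 for pairs with SSB, that gate gave 90.2% with SSB equal to water and 89.2% midway, against about 90.4%. Gating on the largest |t| avoids this. The stepwise rule is also not defined for a distance-based community comparison, so it should not be extended to beta diversity.
- **Intervals and the Benjamini-Hochberg layer.** That layer ranks p-values, so a bare reject-or-not rule would not fit; adjusted p-values are needed. The loss of agreement between tests and simultaneous intervals is a real, small cost, because the aim is to show how close NSBs are to water.

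**Conclusion.** This is an inexpensive improvement worth prespecifying, and no defect in the plan's validity. For glucose iAUC at alpha 0.025, a closed test raises NSB-water power from 90.4% to about 94-95% if the SSB mean equals or lies outside the other two, and to about 91-92% if it lies between them, with the same familywise control within the outcome. The figures rest on the plan's own inputs, two-sided tests, complete data on 60 and equal correlations. How pairwise results enter the truncated Benjamini-Hochberg step is undefined in the plan and was not modelled.

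Three stronger readings are tempting, and the documents do not support them:
- **That 94-95% is the expected power.** It is conditional on the position of SSB, for which only Hypothesis 2 gives a direction.
- **That Tukey-Kramer costs about a fifth more participants.** At 90% power, ((2.645 + 1.282) / (2.270 + 1.282))² = 1.22, but this compares Tukey-Kramer with a wholly unadjusted t-test. The closed test must also pass its first step, so the figure is an upper bound.
- **That the loss is larger for secondary outcomes.** Their lower starting alpha of 0.0125 suggests it, but without means and SDs it cannot be shown.

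**What to change.** In section 11, for glucose iAUC and for the secondary outcomes analysed by mixed model, replace the pairwise sentence with:

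> The largest of the three absolute pairwise t-statistics is first compared with the Tukey-Kramer critical value at the alpha allotted to that outcome. If it is significant, the other two pairs are tested with unadjusted model-based t-tests at the same alpha; otherwise no pair is declared different. The adjusted p-value for each pair is the larger of the Tukey-Kramer p-value for the largest |t| and that pair's unadjusted p-value, and these adjusted p-values are used in the truncated Benjamini-Hochberg procedure.

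Add a line saying which intervals are reported (simultaneous Tukey-Kramer or plain model-based) and that they need not match the second-step tests. Leave beta diversity out of this rule. Make the change before the treatment codes are opened to the blinded statistician. The cost is a short SAP edit, with no new data or participants; the one downside is that simultaneous intervals will sometimes include zero where the second-step test is significant.

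### Does the plan give up multiplicity control over the secondary outcomes when both primary outcomes fail?

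*Combined protocol and SAP*

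**What the plan says.** Section 10.04 sets up a truncated Benjamini-Hochberg procedure with parallel gatekeeping. Part of the alpha left over from the primary family "is reserved for passing to the secondary outcome family if any of the primary outcome is significant". The lowest level at which the secondary family can start is given as 0.0125. The primary step levels in the power table are 0.0375 for UniFrac distance and 0.025 for glucose iAUC.

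Section 11 has two branches for the five secondary outcomes (weight, waist circumference, fasting glucose, 2-hour glucose and the Matsuda index):

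- **Gate open.** The procedure is used to "correct for multiple comparisons for all secondary outcome comparisons [33] if at least one primary outcome reaches significance".
- **Gate closed.** "If none of the primary outcomes reach significance, the secondary outcomes will be analyzed as exploratory variables with no adjustment for false discovery rate".

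Two further provisions in section 11 matter. The listed exploratory outcomes are also analysed without false-discovery control. Tukey-Kramer adjustment, or another suitable method, is named for the pairwise comparisons of the three beverages within each secondary and exploratory outcome, whatever the primary results.

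**The concern.** Under gatekeeping, a family behind a closed gate has no alpha to spend. A sentence that lifts the adjustment just when the gate closes therefore looks backwards. A p-value of 0.04 for body weight would fail after one primary success, yet would fall below a nominal 0.05 with no further adjustment after two primary failures.

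At stake is selective emphasis. A trial with two null primary outcomes is the one in which attention is most likely to move to a secondary result. If unadjusted p-values were then presented as findings, the scheme in section 10.04 would give no protection.

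**Working it through.** **Inputs.** The primary step levels 0.025 and 0.0375 come from the power table in section 10.04, and the lowest secondary level 0.0125 from its text. The five secondary outcomes are listed in section 10.11, and the two branches are in section 11. Four things are assumed: a family alpha of 0.05, a truncation fraction of 0.5, one test per secondary outcome, and a nominal level of 0.05 in the closed-gate branch.

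**1. Reproduce the plan's alphas.** For the i-th smallest of m p-values, the truncated Benjamini-Hochberg level is γ·α·i/m + (1 − γ)·α/m. With α = 0.05, γ = 0.5 and m = 2:

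- i = 1: 0.5 × 0.05 × 1/2 + 0.5 × 0.05/2 = 0.0125 + 0.0125 = 0.025
- i = 2: 0.5 × 0.05 × 2/2 + 0.5 × 0.05/2 = 0.025 + 0.0125 = 0.0375
- Left over if exactly one primary is rejected: 0.05 − 0.0375 = 0.0125

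All three stated figures are returned exactly. Fractions of 0.25 and 0.75 would leave 0.01875 and 0.00625, so 0.5 is the value of the three that fits.

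**2. Thresholds for the secondary outcomes.** Ordinary Benjamini-Hochberg over five outcomes uses α·i/5.

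| Primary outcomes significant | Alpha passed | Smallest p-value must reach | Largest p-value must reach | Status of the secondaries |
|---|---|---|---|---|
| Two | 0.05 | 0.05/5 = 0.01 | 0.05 | Confirmatory |
| One | 0.0125 | 0.0125/5 = 0.0025 | 0.0125 | Confirmatory |
| None | 0 | No threshold stated | No threshold stated | Exploratory |

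If 0.05 is read into the last row, it is 0.05/0.0025 = 20 times looser for a lone effect than after one success, and 0.05/0.01 = 5 times looser than after two. After two successes the difference vanishes when all five p-values are at most 0.05, because the procedure then accepts all five.

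**3. Chance of at least one nominal false positive.** With five independent null outcomes at 0.05 this is 1 − 0.95^5 = 0.226. Simulation (400,000 draws, five equally correlated tests, no true effects) gives:

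| Correlation | Unadjusted at 0.05 | Benjamini-Hochberg at 0.05 | Benjamini-Hochberg at 0.0125 |
|---|---|---|---|
| 0 | 22.6% | 5.0% | 1.3% |
| 0.3 | 20.9% | 4.9% | 1.3% |
| 0.5 | 18.2% | 4.5% | 1.2% |
| 0.7 | 14.9% | 3.9% | 1.1% |

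These figures take the pairwise adjustment within each outcome as holding its level.

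**4. What the rows license.** The first two rows of the threshold table support confirmatory statements about secondary outcomes. The third supports none: section 10.04 passes no alpha without a primary success, and section 11 moves the outcomes into the exploratory class. The 20-fold ratio therefore compares a confirmatory threshold with a descriptive p-value, and these do not lead to the same claim. The chance of a false confirmatory secondary claim after a closed gate is zero as long as the label is respected.

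**The case for a change.** The strongest reply is that a label does not bind anyone. Nothing in section 11 says that p-values after a failed gate are nominal, that significance will not be claimed, or that results are limited to estimates and intervals. Section 9 states directional hypotheses for weight and for glucose and insulin regulation, and section 12 expects the results to inform dietary guidelines. A nominally significant weight result could well be read as a finding, and one sentence would rule that out.

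The omission is real and the sentence would be harmless. But it would only spell out what exploratory status already means. The five outcomes and the reclassification are both fixed in advance, so a reader can see when the label has been ignored. Nor is all multiplicity control removed: the within-outcome pairwise adjustment stays in every branch. Its open wording is a separate matter and does not depend on whether the gate is open.

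A firmer remedy, Benjamini-Hochberg adjustment over the five outcomes at 0.05 after a failed gate, would gain little. A lone effect would then need 0.01, still 0.01/0.0025 = 4 times looser than after one primary success, so the inversion would remain. It would also hold these outcomes to a stricter rule than the other exploratory outcomes, with which section 11 groups them.

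**Conclusion.** No change follows. Section 11 does lift false-discovery adjustment across the five secondary outcomes when neither primary is significant. At an assumed nominal 0.05, the chance of at least one nominal false positive is then about 15% to 23% for correlations from 0.7 down to 0. But no alpha is passed, no confirmatory secondary claim is available, and confirmatory error is not inflated. The rule is an ordinary closed gate.

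What is left is a missing detail of reporting that an analyst would fill sensibly, by giving estimates with 95% confidence intervals and treating any p-values as nominal. The conclusion depends on the exploratory label being respected. It does not depend on the inferred family alpha or truncation fraction, because nothing is passed when no primary succeeds.
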